Appendix 2: Toxicity Severity Scale36

TABLE OF ABBREVIATIONS

AIDS	Acquired immunodeficiency Syndrome
ART	Antiretroviral therapy
BDS	Beck Depression Inventory Score
DHHS	Department of Health and Human Services
FDA	Food and Drug Administration

G-CSF	Granulocyte colony stimulating factor
HCV	Hepatitis C virus
HIV-1	Human immunodeficiency virus type 1
HRPP	Human Research Protection Program
IRB	Institutional Review Board
INF	Interferon
NCI	National Cancer Institute
NIAID	National Institute of Allergy and Infectious Diseases
NIH	National Institutes of Health
NNRTI	Non-nucleoside reverse transcriptase inhibitor
PBMC	Peripheral blood mononuclear cells
PEG	Polyethylene glycol
PEG-INTRON	Pegylated interferon alpha 2b
PI	Principal investigator
PrI	Protease inhibitor
SCA	Single copy assay (viral RNA)

Précis

As a result of combination antiretroviral therapy (ART), morbidity and mortality from acquired immunodeficiency syndrome has declined significantly in the past 15 years, at least in developed countries. Human immunodeficiency virus type 1 (HIV-1) infected individuals now live longer, but must undergo continuous therapy that has substantial consequences on quality of life.

ART suppresses HIV-1 viremia below the limits of detection in current commercial assays (c. 50 copies/mL plasma), but HIV viremia persists even after prolonged suppressive therapy. The origin of this residual viremia is yet not clear, but data suggest that production from long lived HIV infected cells may contribute to viremia. Antiretrovirals are extremely active against replicating cells, and can thus successfully stop viral replication, but have no effect on long-lived viral reservoirs of cells already infected with HIV-1 at the time antiretroviral therapy is initiated. As a result, new strategies are necessary to reduce or eradicate long-lived reservoirs. Interferon alpha is a natural cytokine with antiviral activity. Prior to the introduction of antiretroviral therapy, several studies demonstrated modest effect of interferon alpha in HIV-1 viremia in active cycles of infection in infected individuals. Interferon alpha was also effective *in vitro* in decreasing virus production from cells chronically infected with HIV-1. With the introduction of potent antiretroviral therapy, interferon was not developed as a direct anti-HIV drug. Interferon alpha is relatively effective in therapy of hepatitis C virus (HCV) infection, and has been used in HIV-1/HCV coinfecting individuals. Kottlilil and coworkers in the Laboratory of Immunoregulation NIAID have shown a decrease in HIV-1 RNA levels in HCV coinfecting participants treated with pegylated interferon alpha and ribavirin. In stored samples from that study, we conducted a retrospective trial on samples from participants with HIV-1 RNA levels of <50 copies/mL, showing a further reduction in residual viremia using an ultrasensitive Single Copy Assay (SCA) developed in our laboratory. As such the effects of interferon on HIV viremia and cell associated HIV RNA are of growing interest.

In this protocol we will conduct a prospective, non-randomized, single arm, pilot study to investigate the effect of pegylated interferon alpha 2b on HIV-1 RNA levels as an additional drug in participants undergoing suppressive antiretroviral therapy with viral RNA levels suppressed to less than 50 copies/mL plasma. As patients may have levels of HIV RNA that are lower than our limit of detection, we will also investigate levels of HIV nucleic acid species in cells as well We will determine whether interferon alpha therapy will reduce residual viremia or cell associated HIV RNA in participants on suppressive ART, which will expand our understanding of persistent low-level viremia and the pathogenesis of HIV in infected individuals.

1 Introduction

The human immunodeficiency virus type 1 (HIV-1) is responsible for the development of acquired immunodeficiency syndrome (AIDS) that results in progressive immune system deterioration and death. Therapy treating HIV (antiretroviral therapy or ART) by inhibiting viral replication and allowing immune restoration, has dramatically reduced AIDS-related mortality, but is not curative (Palella, Delaney et al. 1998, Egger, May et al. 2002). After introduction of ART, viral RNA levels in the blood decline significantly. The decay of HIV-1 replication in the presence of an effective ARV follows a biphasic pathway (Shen and Siliciano 2008): a first rapid decay of the cells that produce >90% of plasma virus is followed by a second slower decline in viremia. Several studies have demonstrated that virus declines in plasma because new rounds of virus replication are interrupted by ART and because the cells producing virus die. As a result, the decline in viremia reflects the death rate of virus-infected cells. The first phase of decline in viremia involves mostly activated CD4+ T lymphocytes that have a very short life, surviving only about 1 day; the second phase involves mostly infected macrophages and partially activated CD4+ lymphocytes that have an half life of about 2 weeks.

Decline in viremia is measured by commercially available assays that measure HIV-1 RNA. The current limit of plasma HIV-1-RNA detection is 50 copies/mL, and this is the threshold that international guidelines use as the gold standard for therapy efficacy (Clumeck, Pozniak et al. 2008, DHHS 2008). Using ultrasensitive HIV-1 RNA assays, with sensitivity of HIV-1-RNA down to 1 copy/mL, it is possible to detect persistent HIV-1 viremia even in participants undergoing successful treatment for prolonged periods with ARV (Di Mascio, Dornadula et al. 2003, Maldarelli, Palmer et al. 2007). In participants who have undergone an effective ARV regimen for 7 years, we showed an additional third and a fourth phase of viral decay in these participants.

The set point of residual viremia is predicted by the pre-therapy HIV-1 RNA level; participants with pre-therapy HIV-1 RNA levels greater than 100,000 copies/mL had persistent detectable HIV-1 RNA levels over time (Palmer, Maldarelli et al. 2008). The origin of this residual viremia is uncertain. One possible source is an ongoing replication of viral strains spreading infection to uninfected cells (Zhang, Ramratnam et al. 1999, Havlir, Strain et al. 2003). Ongoing replication may occur if drug therapy does not completely inhibit virus replication, or if virus replication takes place in anatomic sanctuary sites in the body where antiretroviral drugs do not penetrate. Alternatively, HIV-1 may be produced from viral genomes integrated in cells from long-lived HIV-1 reservoirs (Palmer, Maldarelli et al. 2008, Shen and Siliciano 2008). Antiretroviral intensification studies revealed no decrease in HIV RNA levels after introduction of an additional potent antiretroviral (Dinso, Kim et al. 2009, McMahon, Jones et al. 2010, Besson, McMahon et al. 2012), suggesting ongoing replication was not the source of persistent HIV present during therapy. Increases in 2LTR circles in some patients suggest that low level replication events may occur in some patients (Buzon, Massanella et al. 2010, Hatano, Hayes et al. 2011, Hatano, Strain et al. 2013). These data suggest that although replication events may occur, the predominant source of persistent viremia during therapy

is chronic viral production from long-lived cells, and strategies other than conventional antiretroviral therapy are needed to eradicate HIV-1 from infected individuals. In order to investigate the nature of the HIV-1 reservoir we plan to use the intensification strategy with novel antiretroviral therapy.

One possible candidate in this strategy is the antiviral immune modulator interferon alpha (INF). Interferon alphas (interferon-alpha 2a and 2b) are a class of compounds known for their antiviral, immune-activating and immune-suppressing properties (Tilg 1997, Patel and McHutchison 2001, Tilg and Kaser 2004, Stetson and Medzhitov 2006). The addition of polyethylene glycol (PEG) to interferon increases its half-life in the body. PEG-Interferon alpha 2b, administered with ribavirin, is Food and Drug Administration (FDA)-approved for the treatment of chronic hepatitis C. Several clinical trials have shown its efficacy (especially in association with ribavirin) against HCV (Lindsay, Trepo et al. 2001, Manns, McHutchison et al. 2001). In addition, interferon alpha 2b is FDA-approved for the treatment of: hairy cell leukemia, malignant melanoma, follicular lymphoma, condylomata acuminata, AIDS- related Kaposi sarcoma, and chronic hepatitis B and C. In vitro studies conducted with HCV-infected cell-culture systems showed that INF exerts its activity by inducing a non-virus-specific antiviral state within the cell by activating a number of INF-responsive genes (Sen 2001, Bekisz, Schmeisser et al. 2004, Jiang, Guo et al. 2008). Exogenous administration of INF has a similar inducing effect, leading to a rapid reduction of HCV-RNA levels (Guo, Bichko et al. 2001, Zhu, Zhao et al. 2003). Treatment with INF 2b or its pegylated form and ribavirin resulted in a successful clearance of hepatitis C in infected participants (Lindsay, Trepo et al. 2001, Manns, McHutchison et al. 2001), and the level of expression of genes related to INF response, immune cell signaling, defense response, and cell death has been associated with treatment outcome (Lempicki, Polis et al. 2006).

With respect to HIV, INF has shown antiviral activity both in vitro (Ho, Hartshorn et al. 1985) and in vivo (Lane, Kovacs et al. 1988, Hatzakis, Gargalianos et al. 2001). The major activity of INF against HIV is thought to be the inhibition of the release of progeny virions from host-infected cells (Poli, Orenstein et al. 1989, Gottlinger, Dorfman et al. 1991). This anti- HIV-1 activity is opposed by the viral protein Vpu (Gottlinger, Dorfman et al. 1993) and recently the cell protein that mediates viral retention was identified as an INF-induced protein, Bst-317 or tetherin (Neil, Zang et al. 2008). In addition it is known that retroviral restriction factors such as APOBEC3G and TRIM5 α are INF-regulated genes and their induction might also play a role in INF antiviral activity (Goff 2004). A number of in vitro studies suggested that the effects of interferon were modest (2-8 fold reductions in viral RNA) but interestingly, the combination of interferon and early antiretrovirals, such as AZT, was markedly synergistic (Hartshorn, Vogt et al. 1987), including in vitro models of cells chronically infected with HIV-1. These results are particularly intriguing because in cultures of chronically infected cells, the majority of the cells produce HIV-1 from integrated proviruses, and there is little spreading infection; as a result, AZT has minimal or no direct antiviral effect, and interferon may have been the most potent antiviral in these experiments (Poli, Orenstein et al. 1989). Experiments with HIV-1 production from chronically infected cells may represent a

useful model for participants suppressed on antiretroviral therapy as experiments suggest the majority of the detectable virus is produced from cells with integrated proviruses. Although interferon has been studied in active spreading infections, little data are available from participants who are already suppressed on ARV.

In the pre-ART era, INF clinical trials showed a degree of efficacy in reducing viral replication, p24 production, and slowing progression to AIDS (de Wit, Schattenkerk et al. 1988, Lane, Davey et al. 1990, Berglund, Engman et al. 1991). After development of combination ARV, however, INF was not developed as an antiretroviral, due to lower antiviral efficacy, inconvenient route of administration, and adverse effects (Lane, Davey et al. 1990, Dusheiko 1997). Recently, several groups have shown a substantial HIV RNA reduction in participants treated with the pegylated form of interferon alpha (PEG-INF) as part of chronic hepatitis C therapy (Torriani, Ribeiro et al. 2003, Talal, Shata et al. 2004, Neumann, Polis et al. 2007). In addition, Asmuth and colleagues recently studied the effect of pegylated interferon alpha on HIV viral load in HBV/HCV seronegative HIV-1-infected participants who were not receiving antiretroviral therapy. HIV-1 viremia declined by a mean 0.77 log₁₀ copies/mL over 12 weeks (Asmuth D 2009).

The mechanism of interferon effect on HIV viremia is uncertain. There is a substantial literature regarding the effects of interferon in retroviruses in vitro, and in HIV in particular (Pitha 2011). Interferon may induce expression of a number of innate immune responses, which have direct effects on a number of distinct steps in virus replication. Induction of the cellular gene APOBEC 3G and 3F can result in hypermutation of the HIV genome during reverse transcription (Goila-Gaur and Strebel 2008). Induction of the gene tetherin results in retention of HIV on the surface of infected cells and decreases in production of extracellular HIV virions (Perez-Caballero, Zang et al. 2009). The effects of interferon may be manifest as a decrease in peripheral viremia, and a corresponding accumulation of HIV RNA intracellularly.

Much of the information available regarding the effects of interferon in HIV infection has been obtained in patients co-infected with HCV. We performed a retrospective analysis of HIV-1 RNA levels in plasma stored from HIV-1/HCV coinfecting participants enrolled in NIH clinical trials for chronic hepatitis C treatment. We selected participants undergoing antiretroviral therapy with HIV-1 viral RNA suppressed to <50 copies/mL, and used only samples that were obtained within 4 months of initiating therapy. Plasma HIV-1 RNA from 5/6 participants undergoing interferon/ribavirin therapy was decreased in 5/6 participants. In this retrospective pilot study, we could not distinguish whether the decrease in viremia resulted from therapy with interferon or ribavirin, or the combination. Prior clinical studies have indicated no evidence of anti-HIV-1 activity of ribavirin, suggesting that interferon may represent the active agent responsible for this result. Although the number of participants is small, these findings suggest that INF might decrease HIV-1 RNA levels in participants undergoing a successful ARV regimen.

There are limited data on the in vivo effects of interferon alone in individuals undergoing antiretroviral therapy. Montaner et al., studied the effects of pegylated interferon on plasma HIV RNA in individuals undergoing antiretroviral therapy who underwent a structured ART interruption (Azzoni, Foulkes et al. 2013). Decreases in cell associated HIV DNA were detected in a subset of patients; no differences in

plasma HIV levels were detected (using an assay with a 4-5 copy limit of detection ,approximately 30 fold higher than the single copy assay. Differences in levels of cell associated DNA were detected, but no studies of intracellular HIV RNA were performed(Azzoni, Foulkes et al. 2013).Recently intracellular HIV RNA may be recognized by intracellular toll like receptors,which are themselves induced by interferon. As such the effects of interferon on cell associated HIV RNA are of growing interest. Recently we have developed digital droplet methods to quantify HIV RNA levels in infected cells, including levels of unspliced, spliced, and short (tat⁻) transcripts, which may be synthesized in latently infected cells not producing full length HIV RNA. In combination with single genome sequencing, these approaches will be useful in investigating the effects of interferon alpha in HIV infected individuals, including determining overall levels of cell associated RNA, numbers of cells producing HIV RNA, and phylogenetic analysis of HIV RNA sequences in plasma and cells. This advance will permit us to investigate the effects of interferon in patients with and without detectable levels of HIV RNA in plasma; patients with levels of HIV RNA below levels of single copy detection are still be detectable by measurements of HIV RNA .

In the present protocol, we will investigate the effects of interferon alpha 2b in reducing low level HIV viremia. We plan to conduct a non-randomized, open-label, single arm, pilot clinical trial of participants with viremia suppressed on antiretroviral therapy to investigate whether the addition of interferon alpha 2b therapy for 1 month (1.5 µg/kg interferon alpha 2b subcutaneously weekly for a total of 4 doses) results in changes in HIV-1 RNA levels in plasma or in peripheral blood lymphocytes. For the purposes of this pilot study, we will study 10 patients with suppressed viremia. Previously, we have obtained useful information regarding the effects of PI, NNRTI, and raltegravir intensification on HIV-1 viremia using this sample size. In the study planned here, we will perform gene expression studies to characterize the cellular response to interferon therapy in HIV infection. We will investigate potential correlations between expression of interferon-inducible genes and response. We will be particularly interested in the relationship between the interferon responsive gene, tetherin (Perez-Caballero, Zang et al. 2009), and the response to interferon.

2 Objectives

2.1 Primary Objective

This is a non-randomized, single arm pilot study of 10 participants to investigate the effect of interferon alpha on HIV-1 production in plasma and peripheral blood lymphocytes from HIV-infected individuals with HIV-1 RNA levels below the limit of detection in commercial assays.

2.2 Secondary Objectives

The secondary objectives of this study are the following:

1. Investigate HIV-1 genetic variation in individuals undergoing interferon therapy.

2. Investigate the safety and tolerability of PEG INF 2b in HIV-1 infected individuals taking FDA-approved antiretrovirals in combinations recommended by Department of Health and Human Services (DHHS) guidelines.

This study will allow us to elucidate the relationship between the viral decay in response to treatment intensification in HIV-infected individuals with residual viremia on antiretroviral therapy. This information will provide further clarifications on the origin of residual viremia and could provide clues to the eradication of HIV-1 infection.

This is a 48-week study to evaluate the effect of administering interferon alpha 2b to individuals in with viral RNA levels <50 c/ml undergoing antiretroviral therapy. Individuals entered into the study will viral RNA and PBMC sampling determinations prior to interferon intensification. During the second phase of the study, they will receive pegylated interferon alpha 2b (PEG-INTRON) at a dose of 1.5 µg/kg subcutaneously once weekly for 4 weeks starting at Study Entry, then at Visits 1, 2, and 3, for a total of 4 doses. During the interferon intensification phase, participants will continue to receive their standard of care HIV regimen. Following completion of the interferon dosing, participants will be monitored through 48 weeks and will remain on their standard HIV regimen. During all phases, participants will be assessed for viremia using standard and single copy viral load assays. In addition, CD4 and CD8 counts as well as interferon levels will be measured.

3 Study Overview

3.1 Specific Aims

The goal of this study is to investigate the ability of pegylated interferon alpha 2b to reduce residual viremia or cell associated HIV RNA in HIV-infected individuals who are receiving antiretroviral therapy. Viral RNA load will be measured using the sensitive single RNA copy per milliliter assay.

We will also delineate the safety and toxicity profiles of pegylated interferon alpha 2b when co-administered with antiretroviral therapy in HIV-1 infected individuals.

3.2 Study Design and Methods

3.2.1 Study Population

Ten evaluable HIV-1 chronically infected individuals with viremia suppressed to below the limit of detection, on antiretroviral therapy will be enrolled in this trial. Individuals with CD4 counts greater than or equal to 300 cells/µL at screening will be eligible to participate. We plan to conduct this study at the National Institute of Allergy and Infectious Diseases (NIAID)/CCMD Clinic at the National Institutes of Health (NIH) Clinical Center, and at the AIDS Clinical Trials Unit, Division of Infectious Diseases, University of Pittsburgh (active enrollment at Pittsburgh was completed in 2014).

3.2.2 End Points

Unless unacceptable drug-related toxicities emerge (see Appendix 2), clinical contraindications unrelated to drug therapy develop that compromise the health or safety of study participants, or one of the specific criteria for withdrawal from the study is met, all participants will be treated for 4 weeks. Participants will be followed through Week 48.

3.2.2.1 Primary End Points

We will compare viral RNA levels in blood and peripheral blood lymphocytes drawn before, during, and after intensification, including comparison of absolute values of viremia, as well as changes in viremia and area under the curve analyses to detect whether increases or decreases of viremia occurred as a function of interferon therapy. Standard analyses will be included.

3.2.2.2 Secondary End Points

In participants with detectable and amplifiable virus, HIV-1 genetic sequencing will be performed to determine whether interferon therapy results in differences in population structure during the 4-week intensification period. HIV RNA and DNA levels will be investigated using quantitative PCR approaches, including digital droplet PCR. The safety and tolerability of single agent interferon will be assessed through standard clinical management.

3.2.3 Sample Size

As described below (see Statistical Considerations) we expect that 10 participants completing the study will be necessary to yield useful clinical information. In order to enroll 10 participants for this study, we will be screening up to 65 individuals. Any dropouts and non-adherent participants will be replaced.

3.2.4 Safety Analyses

All safety data including adverse events, deaths, vital signs, physical examinations, discontinuations from study drug, and clinical laboratory measurements (hematology, serum chemistry, and urinalysis) will be listed and summarized, using the mean, standard deviations, and percentiles for continuous variables and frequencies and percentages for categorical variables. Any notable values will be flagged. Any comparisons with respect to safety parameters from baseline will be made using the same procedures described above for endpoint analyses.

4 Subject Selection

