5.3 Pre-Entry Visit 2: Leukapheresis Visits (Day -14 to Day -1, Day 28)

Once the subject has been found to meet the eligibility criteria, the subject will return for leukapheresis for the purposes of peripheral blood lymphocyte (PBL) storage for use in future virologic and immunologic studies. Leukapheresis, will be scheduled to occur at Pre-Entry 2 and during Visit 4 (Day 28).

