8.2 Toxicity Management

Specific expected toxicities lower than grade 4 will be managed as follows:

Adverse Event Action

Neutropenia	Participants who experience Grade 3 neutropenia will receive filgrastim at 300 µg subcutaneously up to 3 times a week. Absolute neutrophil counts will be monitored until return to subject's baseline or <Grade 1. Patient will be asked to return in 1-3 days for evaluation. If grade 3 neutropenia has resolved, patient will return 2-3 days later for repeat evaluation. If grade 3 neutropenia has not resolved at the day 1-3 visit, additional G-CSF will be administered
-------------	--

and the patient will return daily for evaluation and additional G-CSF as medically indicated until resolved. Filgrastim will be discontinued at this time. Interferon will be continued for Grade 3 neutropenia.

CD4 cell count	If the CD4 count declines to <14%, pneumocystis prophylaxis will be offered until the percentage of CD4 cells increases to ≥14%.
Depression	If a BDS score of 14-19 is reported, assessment by the site investigator will be scheduled before the next dose of study drug. If a BDS score of 20-28 is reported, a psychiatric evaluation is required before the next dose of study drug. If a BDS score is >29 or suicidal ideation is reported, participants will permanently discontinue study drug and undergo prompt psychiatric evaluation.

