9.5 CD4 Counts

CD4 counts (absolute number and percentage) will be measured at Pre-entry, Entry, Visits 1, 4, 8, 9 and the Final Study or Discontinuation Visit. Samples will be processed according to standard flow cytometry procedures.

10 Statistical Considerations

This pilot study will investigate whether pegylated interferon alpha2-b will reduce residual HIV-1 RNA in participants with HIV-1 viremia suppressed below detectable levels as measured by commercial assays. Two relevant questions are: 1) does intensification reduce viremia in a consistent way across different patients, and 2) are there *any* patients in whom intensification reduces viremia? The first question is of primary interest, and it pertains to the population. The second question concerns whether individual intensification responders can be identified. It is possible to find no consistent pattern across patients, yet identify one or more patients in whom the pattern of viremia lowering over time convincingly rules out a flat slope for that patient. Therefore, analyses will be directed at both population responses and individual responses, with the primary emphasis being on the former.

For both population and individual analyses, one complication is that because patients are selected on the basis of low baseline viral loads, regression to the mean would cause subsequent viral loads to be somewhat larger, in the absence of intensification. To account for this, we will use one baseline measurement to determine eligibility and another to assess changes over time.

The primary analysis (which is at the population level), compares the viral loads obtained from the pre-intensification control period to the week 4 value using a paired t-test. A sensitivity analysis will use the nonparametric Wilcoxon signed rank test to analyze these baseline to week 4 changes. Another analysis computes the slope of viral load over time for each patient, and uses a 1-sample t-statistic and confidence interval to estimate and test whether the average slope is 0.

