Secondary analyses will attempt to identify individual intensification responders. One definition of responder is whether the patient had at least a 1-log decrease from baseline to 4 weeks in viral load. Because patients with baseline viral load below 10 cannot achieve this, another method will compute the least squares slope of viral load versus time for each patient and declare patients with statistically significant slopes as responders. Because the goal for this analysis is to summarize the response of a given individual, we treat the data as independent observations from that patient. This is the same assumption made when using a mixed model, namely that conditioned on the random, patient-specific intercept and slope, the observations are independent. For both the 1 log method and significant slope method of identifying individual responders, we attempt to find differences in baseline characteristics between responders and non-responders, though very low power precludes finding any of these statistically significant unless they are huge. Of particular interest is whether baseline viral load predicts responder status. As described above, for this analysis we will use one baseline value to characterize baseline viral load and another for the calculation of slope to identify responder status.

All tests will be two-sided and an alpha level of less than 0.05 will be considered statistically significant. Analyses will be performed on both intent-to-treat and as per protocol participants. Any dropouts and non-adherent participants will be replaced. We do not feel that stopping criteria are necessary as this pilot study is not for prognosis or clinical management; there is no blinding of study treatment and we will be monitoring toxicities in real time. In this study, we will be studying participants on an ongoing basis, and no interim analysis is planned.

11 Sample Size Estimation

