12.1.4 Potential for Adverse Effects from Leukapheresis

Risks associated with leukapheresis are similar to those seen with whole blood transfusions. They rarely include infection (<1% of persons) and commonly include nausea, fainting, dizziness, bruising at the needle puncture site, blood loss, and a transient decrease in platelet or red blood cell counts in 10% to 25% of persons. Potential problems of a leukapheresis procedure when citrate is given intravenously as an anticoagulant rarely includes seizures in <1% of persons and commonly includes muscle cramping, numbness, chilling, tingling sensations, and feelings of anxiety. Citrate is approved by the Food and Drug Administration for this use. If citrate/heparin or heparin alone is used as the anticoagulant, there may be a transient increase in clotting time, which may lead to blood loss in very rare instances (<1%). There is also a small risk of technical problems with the apheresis machine (1:1000 phereses).

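### Change-from-baseline blood counts under 3.2.4 do not isolate interferon: filgrastim pulls treated participants' Day 28 neutrophils toward no toxicity, and leukapheresis can shift platelets and red cells either way

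*Combined protocol and SAP*

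**What the plan says.** Section 3.2.4 has all safety data listed and summarized, with notable values flagged. It then adds: "Any comparisons with respect to safety parameters from baseline will be made using the same procedures described above for endpoint analyses". It defines no safety baseline and mentions neither filgrastim nor leukapheresis.

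The endpoint procedures stand in two places. Section 3.2.2.1 compares levels before, during and after intensification, including area under the curve. Section 10 gives the primary analysis, which "compares the viral loads obtained from the pre-intensification control period to the week 4 value using a paired t-test". A signed-rank test serves as sensitivity analysis, and a further analysis uses per-patient slopes. On baselines, section 10 says "we will use one baseline measurement to determine eligibility and another to assess changes over time".

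Two other procedures act on the counts:

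- **Filgrastim.** Section 8.2: "Participants who experience Grade 3 neutropenia will receive filgrastim". Neutrophils are then followed until they are back at the participant's own baseline or below Grade 1.
- **Leukapheresis.** Section 5.3 places it on Day -14 to -1 and on Day 28. Section 12.1.4 counts among its common effects "a transient decrease in platelet or red blood cell counts in 10% to 25% of persons". Section 5.6 lists the blood count and the leukapheresis for the same Day 28 visit and states no order.

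Blood counts are taken at Pre-Entry 1, Day 0 and Days 7, 14, 21 and 28 (sections 5.2 and 5.4 to 5.6). Safety and tolerability form a secondary objective (section 2.2), and section 3.2.2.2 frames them as those of interferon given as a single agent.

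**The concern.** A before/after comparison in one arm attributes the whole change to the drug. That fails when the protocol itself applies other procedures that move the same measurement between the two time points.

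For neutrophils the interference is selective. Filgrastim goes only to those with marked neutropenia, and one of the two end points for monitoring is the participant's own baseline, the very value that the paired comparison subtracts. The participants with the largest interferon effect can therefore contribute some of the smallest changes.

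For platelets and red cells, one leukapheresis precedes the Day 0 count by 1 to 14 days, and the other falls on the week 4 comparison day.

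At stake is whether the mean hematologic changes reported for a secondary objective describe interferon or a mixture of procedures. With ten participants, one or two altered values can move a mean visibly.

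**Working it through.** The documents state no expected count change, filgrastim frequency, or size or duration of the leukapheresis effect. There is therefore no plan figure to reproduce. Everything marked *assumed* below is illustration.

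**1. Neutrophils and filgrastim**

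Let k of n = 10 participants receive filgrastim. Let U be their Day 28 count had they not received it, and R the count observed.

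Shift in mean change = (k/n) x (R - U). This is zero if k = 0, and it points toward no toxicity whenever R > U.

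*Assumed* (x10^9/L): baseline 4.0; untreated participants 2.2 at Day 28; U = 0.7; R = 2 to 8.

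| k | Mean change without filgrastim effect | Shift | Mean change observed |
|---|---|---|---|
| 0 | -1.80 | 0 | -1.80 |
| 1 | -1.95 | 0.13 to 0.73 | -1.82 to -1.22 |
| 2 | -2.10 | 0.26 to 1.46 | -1.84 to -0.64 |
| 3 | -2.25 | 0.39 to 2.19 | -1.86 to -0.06 |

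A second *assumed* set (cells/mm³): baseline 3000, eight participants at 2000, and two at 700 who reach 3000 to 5000. The mean without the filgrastim effect is (8 x 2000 + 2 x 700)/10 = 1740, a fall of 1260. The shift is 0.2 x 2300 = 460 to 0.2 x 4300 = 860, so the observed fall is 800 to 400.

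Dropping the filgrastim recipients does not remove the bias. In the first set the remaining participants show 2.2 - 4.0 = -1.80 whatever k is, because the worst affected have left the average. The lowest on-treatment count does better. If the others' lowest count is their 2.2, then for k = 3 the mean lowest count is (3 x 0.7 + 7 x 2.2)/10 = 1.75, a change of -2.25.

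**2. Platelets, red cells and leukapheresis**

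With 10% to 25% affected (section 12.1.4), 1.0 to 2.5 of ten participants are expected to have a fall after one procedure. The chance of at least one is 1 - 0.90^10 = 0.651 to 1 - 0.75^10 = 0.944. This is the chance of a transient fall at some point, not of a count still low at Day 0.

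*Assumed*: affected persons fall by d = 10% to 30% with no recovery before the count in question; the true interferon fall is 30%. With p the proportion affected, the mean count is too low by p x d = 1.0% to 7.5%.

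- Day 0 baseline still depressed, Day 28 count unaffected: 1 - 0.70/(1 - pd) = 29.3% to 24.3%.
- Baseline unaffected, Day 28 count drawn after leukapheresis: 1 - 0.70 x (1 - pd) = 30.7% to 35.2%.
- Both affected equally: the factors cancel, giving 30.0%.

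The direction thus depends on recovery time and draw order, and the documents give neither.

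**3. Which baseline**

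The Pre-Entry 1 count precedes leukapheresis, because section 5.3 schedules the procedure after eligibility is established. It is also the eligibility value: inclusion criterion 10 sets minima for neutrophils, platelets and hemoglobin within 14 days before enrollment. Values selected for exceeding a minimum tend to be lower on repeat, so this baseline leans toward an apparent fall. The Day 0 count avoids that but follows leukapheresis. Neither is clean.

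**The case against.** The strongest reply is that nothing is hidden. Section 3.2.4 lists all hematology and adverse events. Counts are reviewed before each dose (section 7.3), filgrastim is given only once Grade 3 neutropenia has been found, all adverse events go into the database (section 15.1.2), and concomitant medications are documented (section 6). This stands: the incidence of Grade 3 neutropenia is not masked. What can be masked is the later mean count, its duration and any progression.

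Second, neither Day 0 nor Day 28 is named for safety. The text that literally stands above 3.2.4 is section 3.2.2.1, and the paired test comes later. That Day 0 is the intended baseline is an inference, though a reasonable one from section 10's separation of eligibility and change values. The reply does not rescue the comparison, because a before/during/after or area-under-the-curve analysis would take in post-filgrastim counts too.

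Third, filgrastim may never be used, and it stops on resolution, so its effect may have faded by Day 28. Correct: the bias is then zero or small. The overlap with interferon is also unclear. Section 8.2 continues interferon at Grade 3 neutropenia, while section 8.3 lists Grade 3 or higher neutropenia as grounds for permanent discontinuation. On either reading, a post-filgrastim count is not an interferon-only value.

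A reader might go further and infer that hematologic toxicity as a whole is understated. The documents do not support that. Leukapheresis on Day 28 and research phlebotomy of up to 550 mL per 8 weeks (section 12.1.5) push counts down and would overstate an interferon effect. Section 12.1.4 ties leukapheresis to platelets and red cells only.

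**Conclusion.** Run as written, the comparison of blood counts with baseline does not isolate interferon.

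- **Neutrophils:** the direction is clear. Each participant whose Day 28 count is raised by filgrastim moves the mean toward no toxicity by (R - U)/10. With no filgrastim use there is no bias.
- **Platelets and red cells:** the change is confounded, with no established net direction. Under the assumed drops, a true 30% fall reads anywhere from 24.3% to 35.2%.
- **Adverse events:** Grade 3 neutropenia remains recorded, so the problem lies in the change-from-baseline summaries and tests.

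All sizes rest on assumed counts, rescue values and recovery; only the 10% to 25% and the ten participants come from the documents. This deserves correction because the data needed are already collected.

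**What to change.** In section 3.2.4:

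1. **Neutrophils.** Analyze each participant's lowest count from first dose through Day 28 against baseline, including any lower count after filgrastim, so that a deeper nadir is not discarded. Flag post-filgrastim values, show the week 4 comparison with and without them, and report the number given filgrastim. State that neither week 4 version is unbiased. Report the lowest count descriptively and by grade, since the lowest of several counts tends to fall below a single baseline even without a drug effect.
2. **Draw order.** State that Day 28 blood is drawn before leukapheresis starts.
3. **Baseline.** Name Day 0 as the hematology change baseline, in line with section 10's rule. Add the pre-leukapheresis Pre-Entry 1 count as a sensitivity baseline, noting that it is also the eligibility value and so subject to regression to the mean.

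Separately, sections 8.2 and 8.3 must be reconciled on interferon at Grade 3 neutropenia. No treatment rule is proposed here.

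The cost is a few lines of text and a few extra summaries, with no added visits or samples.
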